## Study Design

Describe and explain the study design (e.g., observational, secondary analysis, single/double blind, parallel, crossover, deception, etc.).

- Clinical Research: Indicate whether subjects will be randomized and whether subjects will receive any placebo.
- Community-Based Participatory Research: If you are conducting community-based participatory research (CBPR), describe strategies for involvement of community members in the design and implementation of the study, and dissemination of results from the study.
- Qualitative research: Indicate ranges where flexibility is needed, if a fixed interview transcript is not available, describe interview topics including the most sensitive potential questions.
- Research Repositories: If the purpose of this submission is to establish a Research Repository (bank, registry) and the material you plan to collect is already available from a commercial supplier, clinical lab, or established IRB approved research repository, provide scientific justification for establishing an additional repository collecting duplicate material. Describe the repository design and operating procedures. For relevant information to include, see the UK Research Biospecimen Bank Guidance or the UK Research Registry Guidance.

This is a double-blind, 12-month pilot study to evaluate of the safety, feasibility, and preliminary efficacy of dorsal myelotomy and expansive duraplasty performed either without or with autologous nerve graft implantation after acute traumatic spinal cord injury. Ten participants will be allocated to receive either DMED (n=5) or DMED + ANGI (n=5) based on a block design. Participants and assessors will be blinded to group allocation. Excess sural nerve samples will be collected for banking/analysis (may include proteomic, culturing, genomic, cellular analysis).

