Fortuitously, neurosurgery and neuroscience colleagues at the University of Kentucky have already established and validated a reproducible source of cellular tissue from the peripheral nervous system,[8, 9] that contain injured-peripheral nerve tissues shown to include a variety of cells that express several key growth factors and repair molecules including glial cell line-derived neurotrophic factor, brain-derived neurotrophic factor, nerve growth factor, and neurotrophin-3. They have implanted ANGI in to the CNS of 80 participants without any serious adverse events related to the study intervention and with the most common study-related adverse event being paresthesias and acute pain at the lateral aspect of the foot and ankle ipsilateral to the biopsy. Amongst other possible cellular neurotrophic sources 9 contained within these grafts, Schwann cells are known to transdifferentiate after injury into an activated repair phenotype through a c-Jun mediated pathway and produce a host of repair and survival promoting neurotrophins and anti-apoptotic factors.[28]

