Surgical Protocol: All subjects will undergo spinal cord decompression and instrumented spinal stabilization through a posterior approach according to standard-of-care guidelines in place at the Department of Neurosurgery, University of Kentucky. The extent of laminectomies will be based on the extent of cord edema as noted on the pre-operating MRI study. All patients will also undergo dorsal myelotomy and expansive duraplasty (DMED) under microscopic magnification. The dorsal dura will be incised longitudinally in the midline with the length once again estimated from the length of the spinal cord edema on the pre-operative MRI. Under high microscopic magnification, the dorsal midline of the spinal cord will be identified to allow for a myelotomy using a microsurgical beaver-blade extending through to the anteroposterior midline. While no attempt will be made to suction or otherwise excise intramedullary spinal cord hematoma, it is understood that spontaneous egress of variable amounts of clotted blood may be noted given the severity of the trauma typically noted in some patients. Following probe insertion (see below), we will then suture an appropriately-sized elliptical patch of artificial dura (e.g., Durepair, Medtronic, Minneapolis, MN) to the dural edges to expand the intradural space. The duraplasty will be supplemented with a patch of fibrin glue (e.g., Tisseel, Baxter, Deerfield, IL).

A total of n = 5 patients will undergo supplemental ANGI procedure in addition to DMED. Once the dorsal myelotomy is completed, the sural nerve will be accessed through a standard neurosurgical approach as employed for biopsy of the sural nerve. A 4 cm incision will

be fashioned starting above the lateral epicondyle and an approximately 2 cm section of the nerve will be excised, placed in normal saline, and appropriately trimmed. Under direct high-magnification microscopic visualization, an approximately 3-5 mm segment (cut into smaller, 0.5 to 1mm segments) of sural nerve/fascicles will be carefully deposited over the dorsal myelotomy site. Great care will be taken to ensure that the subsequent duraplasty is expansive enough such that no additional compressive effect is associated with the ANGI procedure.

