Microdialysis (MD) Setup and Analysis: Microdialysis will be initiated postoperatively in the neurointensive care unit in all enrolled subjects.[12] Central nervous system fluid will be perfused at 0.3 µL/min using the 106 microdialysis pump (M dialysis AB). MD vials will be changed hourly and analyzed using ISCUSFlex (M dialysis AB) for glucose, lactate, and pyruvate. The lactate-to-pyruvate ratio will be calculated. The first two samples from each subject will be discarded to allow priming of the MD catheter and stabilization of the metabolite concentrations. Metabolite levels will be

compared to corresponding hourly averages of ISP, MAP, and SCPP. As noted by other authors [12], we expect that such a MD protocol will measure spinal cord surface metabolism at the injury site, which is thought to correlate with intraparenchymal injury site metabolism.[30]

Post-treatment follow-up: After surgery, subjects will be followed in the neuro intensive care unit and throughout their hospital stay per routine, standard-of-care clinical guidelines for the management of acute SCI. Following hospital discharge, subjects will then undergo assessments in accordance with the study calendar.

Post-treatment follow-up: Day 28 (± 7 days), Day 42 (± 7 days)

Review unresolved AEs

- Record additional AEs/SAEs
- ASIA Impairment Scale

Post-treatment Follow-up: Day 84 (± 14 days), Day 182 (± 14 days) and Day 365 (± 30 days)

- Review unresolved AEs
- Record additional SAEs
- ASIA Impairment Scale
- Spinal Cord Independence Measure (vIII)

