Sural nerve graft harvesting procedures. The surgical risk is minimal and this part of the protocol is considered a minor surgery and employs a surgical approach that is used for sural nerve biopsies. The incision is ~3cm in length located above and behind the lateral aspect of the ankle. The sural nerve is a sensory nerve that supplies sensation to the lateral aspect of foot and heel. Participants in previous studies have reported either a temporary sensory loss or permanent loss of sensation to a small dermatomal patch on the outer aspect of the foot and/or heel. For this participant population, this would not be a concern. Although this study does involve grafting, participants will donate their own tissue. This eliminates the risk of graft rejection and obviates the need for immunosuppressant medications typically used with other transplant studies.

Magnetic Resonance Imaging (MRI): The MRI may be with or without contrast agent and participants may notice discomfort, tingling or warmth in the lips, metallic taste in the mouth, tingling in the arm, nausea, or headache. These symptoms go away quickly. There is also a small risk of an allergic reaction to the contrast agent.

Sedation (Diazepam): Respiratory depression, Suicidality, Dependency and abuse, Bradycardia, Hypotension, Syncope, Depression, Anterograde amnesia, Headache, Nausea, Tremor, Dystonia

Genetic or genomic testing is possible: Even without the participant's name or identifiers, genetic information is unique to them. The results of genetic research apply to both the participant and their family members. Genetic information used improperly to discriminate or support negative stereotypes could cause the participant their family distress. The researchers do not know whether future technology will make it possible for someone to trace the participant's genetic information back to them.

There may be additional risks associated with banking specimen samples such as the risks associated with blood draws and the potential for a breach of confidentiality.

Social Risks: Breach of confidentiality could impact insurability, employability, reproduction plans, family relationships, immigration status, paternity suits, and stigmatization, if applicable.

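### The protocol calls the study double-blind, but only the nerve-graft arm has a leg incision and no sham or concealment is described, so the participant-blinding claim is unsupported

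*Protocol*

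**What the plan says.** Study Design introduces the trial with the words "This is a double-blind, 12-month pilot study to evaluate of the safety, feasibility, and preliminary efficacy" and says of masking: "Participants and assessors will be blinded to group allocation". Ten participants are split five and five between DMED and DMED + ANGI.

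The Surgical Protocol, under Research Procedures, gives decompression, stabilisation and DMED to everyone and then adds: "A total of n = 5 patients will undergo supplemental ANGI procedure in addition to DMED". For those five the sural nerve is reached through a 4 cm incision, which is to "be fashioned starting above the lateral epicondyle and an approximately 2 cm section of the nerve will be excised". The sural nerve paragraph of Potential Risks & Benefits describes it differently: "The incision is ~3cm in length located above and behind the lateral aspect of the ankle". That paragraph also reports, from previous studies, temporary sensory loss or "permanent loss of sensation to a small dermatomal patch on the outer aspect of the foot and/or heel", and then discounts this for the present population. Background, on earlier use of the graft, gives "the most common study-related adverse event being paresthesias and acute pain at the lateral aspect of the foot and ankle ipsilateral to the biopsy".

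Monitoring hardware does not separate the arms. The probe and catheter insertion text is not limited to one arm, and "Microdialysis will be initiated postoperatively in the neurointensive care unit in all enrolled subjects".

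**The concern.** A double-blind label tells later readers that neither the participant nor the person rating the outcome knew the arm. Here one arm has an extra wound on the lower leg and the other does not. Unless something hides or mimics it, a participant can work out the arm by looking, at any time over 12 months. A rater can do so by seeing the leg, reading the operative note or being told.

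The label will outlive this pilot. The title promises preliminary efficacy. Data and Safety Monitoring says the study is not powered for motor and functional outcomes but expects those data to feed power calculations for later phases. Ratings carried forward as double-blind would be given more weight than the described procedures justify.

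**Working it through.** This is a check of the text; no sample size or error rate is involved.

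**1. What each arm receives, as described**

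| Element | DMED (5) | DMED + ANGI (5) | Protocol section |
|---|---|---|---|
| Posterior decompression, stabilisation, DMED | yes | yes | Research Procedures, Surgical Protocol |
| Pressure probe and microdialysis catheter | yes | yes | Research Procedures, probe and microdialysis paragraphs |
| Sural nerve harvest through a leg incision | none described | yes | Research Procedures, Surgical Protocol |
| Nerve kept for banking | none described | excess from the graft | Study Design; Future Use and Sharing of Material |
| Sham incision or concealment | none described | none described | all sections available |

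Banking does not create a matching wound. Study Design banks only surplus nerve, and Future Use and Sharing of Material ties the stored piece to the nerve obtained for grafting and rules out taking extra tissue.

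**2. How completely the wound marks the arm**

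Incision present: 5/5 in DMED + ANGI, 0/5 in DMED. Arm identified by presence or absence: (5 + 5)/10 = 10/10.

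**3. The sensory cue is secondary**

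Foot and ankle paresthesias, pain or numbness could also reveal the arm where sensation is preserved. Eligibility is restricted to AIS A or B, and the protocol itself discounts the sensory loss in these patients. It does so as a statement about risk, and it does not hide a wound or scar. The point therefore rests on the wound.

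**4. Assessor masking**

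Nothing says that the assessors know the arm. Equally, no section names a separate rater, restricts the operative note, covers the leg or asks participants to keep silent. In-hospital ISNCSCI examinations are part of standard care (Objectives, Aim 2). Adverse event review falls at the same visits as AIS and SCIM (Research Procedures, follow-up), so a rater who also reviews events could learn of foot or ankle symptoms.

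**5. Which outcomes are exposed**

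- AIS/ISNCSCI: through a rater who learns the arm.
- SCIM: Data Collection & Research Materials allows either the research team or the participant or representative to supply information on the forms. Some items may come from the participant, and a masked rater would not mask those.
- Adverse event attribution: the investigators judge relatedness to DMED with or without ANGI (Data and Safety Monitoring), and no masking of that judgement is described.
- Little affected: feasibility counts, and the pressure and microdialysis readings. Aim 3, the one stated comparison between arms, uses those readings.

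**6. Visits at which masking steps would apply**

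AIS is rated at Days 28, 42, 84, 182 and 365: 5 × 10 = 50 visits at most. SCIM falls on three of these (Days 84, 182, 365), 3 × 10 = 30, and adds no visit. In-hospital examinations are daily to Day 7, up to 7 × 10 = 70, with weekly ones after that. These are workload ceilings with no missed visits; they do not count unmasked ratings.

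**The case against.** The strongest reply is that the document is incomplete. The Table of Events and consent form are attachments that are not shown, and a concealment step could sit there. Data Collection & Research Materials lists peripheral nerve tissue without naming an arm, which might suggest a harvest in everyone. The first part stands to this extent: the correction should yield if such a step can be cited. It does not rescue the text as it is. The form asks in Study Design whether any placebo is used and in Research Procedures for the procedures of each group, and the answers mention no sham. The unqualified listing of nerve tissue does not override a surgical protocol that assigns the harvest to five patients.

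A second reply is that missing operational detail on assessor masking is not an error. That is fair. A reader might infer that assessor blinding is contradicted, or that the outcome ratings are in fact unmasked. The documents support neither: a rater kept away from the leg, the note and the event record could be masked.

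A third reply is that the consequences are modest: an unpowered pilot whose only stated between-arm aim relies on instruments. This stands and limits the weight of the point. It does not make the label correct.

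**Conclusion.** The participant-blinding claim, and with it the double-blind label, is not supported by the procedures described: the wound or scar identifies the arm for 10 of 10 participants. Assessor blinding is stated without any means of securing it. The consequence is confined to AIS/ISNCSCI, SCIM and adverse event attribution.

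A reader might go further and conclude that the neurological results are biased, or that the pilot is invalid. The documents give no basis for either. They do not show how many ratings would be unmasked, and neither the direction nor the size of any bias can be derived.

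The conclusion assumes that no sham or concealment is specified in the attachments not shown, and that the harvest is performed only where the surgical protocol places it. It is a misdescription of the design that should be corrected, at low cost.

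**What to change.** 1. In Study Design, replace the double-blind label and the participant-blinding claim with *assessor-masked*, unless an existing concealment step in an attachment is cited.
2. Support the assessor claim in the protocol:
   - AIS/ISNCSCI is rated by existing staff who were not in the operating room and do not consult the operative note.
   - The harvest site is covered identically in both arms, with test points left accessible.
   - Participants are asked not to disclose their arm.
   - Adverse event review is done by someone other than the rater, or after the rating.
3. Treat SCIM items supplied by the participant or representative, and the investigators' event attribution, as unmasked when interpreting them.
4. Where no masked rater is available, which may be the case for standard-care examinations in hospital, report those ratings as unmasked.
5. Reconcile the incision descriptions in the Surgical Protocol and in Potential Risks & Benefits. They differ in length (4 cm against about 3 cm) and in how the site is described, and the site determines what a covering has to hide.

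Cost: protocol wording, a leg covering and rater assignment at no more than 50 existing follow-up visits, plus the in-hospital examinations if masking is claimed there. No new visits, patients or procedures are needed. This assumes that a trained rater from outside the operating room can be found, which the protocol does not establish. The downside is a less favourable masking label and minor visit logistics. A covering hides the wound, but not altered sensation at the outer foot or heel where sensation is preserved.

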### Attachments

## Subject Recruitment Methods & Advertising

Describe how the study team will identify and recruit subjects. Please consider the following items and provide additional information as needed so that the IRB can follow each step of the recruitment process.

- · How will the study team identify potential participants?
- Who will first contact the potential subjects, and how?
- Will you use advertisements? If so, how will you distribute those?
- · How and where will the research team meet with potential participants?
- If applicable, describe proposed outreach programs for recruiting women, minorities, or disparate populations.
- How you will minimize undue influence in recruitment?
- Attach copies of all recruiting and advertising materials (emails, verbal scripts, flyers, posts, messages, etc.).

For additional information on recruiting and advertising:

- IRB Application Instructions Advertisements
- PI Guide to Identification and Recruitment of Human Subjects for Research

Potential participants will be those who arrive for treatment from the UK Neurosurgery service/[name]'s patients. A clinical member will introduce the study either to the potential participant or the potential participant's LAR. A member of the study team, authorized to obtain informed consent, will then explain the risk and benefits of participating in the study to the potential participant or LAR.

Researchers may participate in radio or TV/video interviews. General information about their research may be presented with a phone number or website url for more study specify information.

Consenting members of the research team and/or consenting participants may be interviewed about the study for print, radio, or video which may be distributed via the aforementioned activities.

Researchers may participate in patient group presentations where the study may be discussed.

We will ensure that future advertising used during the study will not be implemented until the IRB has reviewed and approved those ads.

To protect confidentiality, all subjects are assigned a unique number, and this number is used for labeling of all samples and the identification of all laboratory material obtained from subjects, and there is no public release of the name of the subject from whom the material was derived. All data are kept in a password protected computer file or in locked filing cabinets.

Attachments

#### **Research Procedures**

Describe how the research will be conducted.

- What experience will study participants have?
- What will study participants be expected to do?
- · How long will the study last?
- Outline the schedule and timing of study procedures.
- · Provide visit-by-visit listing of all procedures that will take place.
- Identify all procedures that will be carried out with each group of participants.
- Describe deception and debrief procedures if deception is involved.

Differentiate between procedures that involve standard/routine clinical care and those that will be performed specifically for this research project. List medications that are explicitly forbidden or permitted during study participation.

We propose that intraspinal pressure management starting at the time of surgical decompression following acute SCI alone, or with ANGI, may ultimately provide a meaningful impact to improve functional outcomes and quality of life. As a first step, we propose to systematically assess the safety and feasibility in this at-risk patient population. We will perform dorsal myelotomy to promote hematoma and necrosis evacuation for patients that have sustained severe acute cervical / thoracic SCI. This will be performed along with expansive duraplasty during standard surgical (bony) decompression with or without autologous nerve graft implantation (ANGI) in 5 participants each (n = 10 total). As a cell-based therapy, ANGI allows for a unique opportunity for prompt intervention at the injury site without the need for immunosuppression.

As part of research, participants will have intrathecal pressure probes and microdialysis catheters inserted at the time of surgery. Each participant will undergo a pre-operative MRI to inform the extent of decompression and dural expansion, and a post-operative MRI on day 2 to confirm that surgical goals were achieved. Continuous monitoring of intraspinal pressures, biochemical profiles, adverse events, ASIA impairment scores, and functional independence measures will be performed from the neurointensive care unit to one year postoperatively.

Screening and Registration Procedures - Participants with suspected acute cervical or thoracic SCI will be screened upon arrival to hospital. As part of the standard of care, these evaluations will occur prior to enrollment:

- Vital signs (Temperature, Blood Pressure, Respiration rate, Pulse, O2 saturation, Height, Weight)
- Physical examination and Medical History
- · Spinal cord injury (SCI) Time, Cause, and Level of injury
- Demographics and Clinical Variables (age, race, gender, and body mass index (BMI)
- Neurological examination including ISNCSCI motor and sensory assessments
- ECG (12-lead)
- · Clinical laboratory tests (complete blood count, chemistry, liver function tests)

Eligible participants will be enrolled and undergo study procedures within the first 48 hours after documented SCI. This injury-toprocedure timeframe appears feasible given the injury-to-admission times reported in recent SCI studies. For instance, in the phase 3 Riluzole study, 94.6% underwent surgical decompression within 24 hours, which was typically preceded by completion of CT and MRI studies.[16]

Study-related Management (standard-of-care) :

• Serial vital signs (temperature, blood pressure, pulse, respiration rate, O2 saturation) and

neurologic (International Standards for Neurological Classification of Spinal Cord Injury - ISNCSCI) assessments

• Blood work; CT scans of the spine and head (as indicated); pre- and post-operative MRI of the cervical/thoracic spine

Cervical / thoracic CT studies will reveal the nature of the associated spinal fracture and/or misalignment. Acute SCI management guidelines, most recently revised by a consensus panel in 2013[14], will be adhered to. These guidelines include avoidance of hypoxia and hypotension with induced hypertension as needed to keep mean arterial pressure = 85mmHg for 7 days. The ability to undergo early surgical intervention, which is increasingly recognized as a standard-of-care intervention,[2] constitutes an inclusion criterion for the study.

Surgical Protocol: All subjects will undergo spinal cord decompression and instrumented spinal stabilization through a posterior approach according to standard-of-care guidelines in place at the Department of Neurosurgery, University of Kentucky. The extent of laminectomies will be based on the extent of cord edema as noted on the pre-operating MRI study. All patients will also undergo dorsal myelotomy and expansive duraplasty (DMED) under microscopic magnification. The dorsal dura will be incised longitudinally in the midline with the length once again estimated from the length of the spinal cord edema on the pre-operative MRI. Under high microscopic magnification, the dorsal midline of the spinal cord will be identified to allow for a myelotomy using a microsurgical beaver-blade extending through to the anteroposterior midline. While no attempt will be made to suction or otherwise excise intramedullary spinal cord hematoma, it is understood that spontaneous egress of variable amounts of clotted blood may be noted given the severity of the trauma typically noted in some patients. Following probe insertion (see below), we will then suture an appropriately-sized elliptical patch of artificial dura (e.g., Durepair, Medtronic, Minneapolis, MN) to the dural edges to expand the intradural space. The duraplasty will be supplemented with a patch of fibrin glue (e.g., Tisseel, Baxter, Deerfield, IL).

A total of n = 5 patients will undergo supplemental ANGI procedure in addition to DMED. Once the dorsal myelotomy is completed, the sural nerve will be accessed through a standard neurosurgical approach as employed for biopsy of the sural nerve. A 4 cm incision will

be fashioned starting above the lateral epicondyle and an approximately 2 cm section of the nerve will be excised, placed in normal saline, and appropriately trimmed. Under direct high-magnification microscopic visualization, an approximately 3-5 mm segment (cut into smaller, 0.5 to 1mm segments) of sural nerve/fascicles will be carefully deposited over the dorsal myelotomy site. Great care will be taken to ensure that the subsequent duraplasty is expansive enough such that no additional compressive effect is associated with the ANGI procedure.

Probe / Catheter Insertion: The ISP probe and microanalysis catheter will be inserted in the operating room. During the standard-ofcare posterior approach, a 14-gauge introducer will be used to separately tunnel an FDA-approved pressure probe (e.g., Codman Microsensor Transducer®, Integra LifeSciences, Princeton, NJ) and an FDA-approved microdialysis catheter (e.g., M dialysis AB, North Chelmsford, MA) intradurally one level below the injury over the surface of the injured cord and tunneled up to the site of maximal cord swelling as noted on the preoperative MRI study.[4] The ISP probe will be calibrated and it along with the catheter will be advanced subdurally, under the operating microscope, through the dural hole until their tips lie at the site of maximal spinal cord swelling according to the MRI scan. The separate slit dural openings will be covered with fibrin glue (e.g., Tisseel®, Baxter, Deerfield, IL). Standard-of-care postoperative CT studies (when available) will be used to confirm in situ probe positioning.

Intraspinal Pressure and Arterial Blood Pressure Monitoring: The pressure catheter will be connected to a Codman ICP Express monitoring device linked via a ML221 amplifier to a PowerLab running LabChart (AD Instruments, Colorado Springs, CO). Standard-of-care continuous arterial blood pressure monitoring will be performed through a radial arterial line, in turn also connected to the PowerLab system. ISP and blood pressure signals are sampled at approximately 1 kHz, and patients are monitored for up to 7 days following SCI. Data will be analyzed using Labchart (AD Instruments, Colorado Springs, CO) and ICM+ (www.neurosurg.cam.ac.uk/icmpl us). Spinal cord perfusion pressure will be calculated as mean arterial pressure (MAP) – ISP. Of

(www.neurosurg.cam.ac.uk/icmpl us). Spinal cord perfusion pressure will be calculated as mean arterial pressure (MAP) – ISP. Of note, ISP will be expected to be different from intrathecal pressure (typically measured in the lumbar spine) as the swollen, injured cord is compressed against the dura thus compartmentalizing the intrathecal space.[29]

Microdialysis (MD) Setup and Analysis: Microdialysis will be initiated postoperatively in the neurointensive care unit in all enrolled subjects.[12] Central nervous system fluid will be perfused at 0.3 µL/min using the 106 microdialysis pump (M dialysis AB). MD vials will be changed hourly and analyzed using ISCUSFlex (M dialysis AB) for glucose, lactate, and pyruvate. The lactate-to-pyruvate ratio will be calculated. The first two samples from each subject will be discarded to allow priming of the MD catheter and stabilization of the metabolite concentrations. Metabolite levels will be

compared to corresponding hourly averages of ISP, MAP, and SCPP. As noted by other authors [12], we expect that such a MD protocol will measure spinal cord surface metabolism at the injury site, which is thought to correlate with intraparenchymal injury site metabolism.[30]

Post-treatment follow-up: After surgery, subjects will be followed in the neuro intensive care unit and throughout their hospital stay per routine, standard-of-care clinical guidelines for the management of acute SCI. Following hospital discharge, subjects will then undergo assessments in accordance with the study calendar.

Post-treatment follow-up: Day 28 (± 7 days), Day 42 (± 7 days)

Review unresolved AEs

- Record additional AEs/SAEs
- ASIA Impairment Scale

Post-treatment Follow-up: Day 84 (± 14 days), Day 182 (± 14 days) and Day 365 (± 30 days)

- Review unresolved AEs
- Record additional SAEs
- ASIA Impairment Scale
- Spinal Cord Independence Measure (vIII)

